A 3. Importance of Measuring Biomarkers: We will evaluate specific biomarkers of smoking-related harm during pregnancy, which may help explain how smoking cessation or reduction increases birth weight and gestational age. Although biomarkers of chemical exposure (e.g., exhaled CO, cotinine, anabasine/anatabine, thiocyanate) can be used to measure tobacco exposure, we believe that it is scientifically important to carefully evaluate potential biomarkers of smoking-related harm (i.e., physiological change biomarkers), because these may help to elucidate the mechanisms by which tobacco cessation/reduction increases gestational age and birth weight [46]. Although many biomarkers have been theorized to contribute to cardiovascular disease, pulmonary disease, or cancer in non-pregnant smokers, none have been shown to predict clinical outcomes, because of the length of time it takes to develop various diseases [46]. Pregnancy is a unique situation that lends itself to the examination of biomarkers of tobacco risk, because of the rapid fetal growth that occurs during a 9-month period.

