Evidence that these biomarkers are mediators of pregnancy outcomes that are affected by smoking has important implications for other pharmacotherapy studies in pregnant smokers by providing surrogate measures of potential risk [46] or in studies of reduced-exposure products (e.g., e-cigarettes, smokeless tobacco) that may be used by pregnant women. Since the FDA has recently been authorized to regulate tobacco products [56] there is likely to be heightened interest in biomarkers of tobacco product risk, particularly in vulnerable populations.

3. Hypotheses, aims and objectives:

Hypothesis 1:

We hypothesize that the nicotine inhaler compared to placebo inhaler will double the 7-day point prevalence abstinence rates (confirmed by exhaled CO) at 32-34 weeks gestation and will reduce the number of cigarettes smoked per day (CPD).

Aims / objectives 1:

To examine the efficacy of the nicotine inhaler compared to a matched placebo for smoking cessation and reduction among pregnant smokers.

Hypothesis 2:

- a) The nicotine inhaler will yield lower cotinine concentrations than placebo at 32-34 weeks gestation.
- b) Infants born to mothers in the NRT group will have higher birth weights and greater gestational age than infants born to mothers randomized to placebo. 2c) Fewer nicotine-treated subjects will deliver a low birth weight (<2500 grams) or a preterm (<37 weeks) infant than those in the placebo group.

Aim/Objective 2:

To compare the nicotine inhaler with placebo on safety measures which include a) overall nicotine exposure (i.e., serum cotinine) and b) birth outcomes (i.e., birth weight and gestational age).

Hypothesis 3: Pregnant women who are heavier smokers (i.e., ≥ 10 cigarettes/day) will be less able to quit with behavioral treatment alone than lighter smokers and the inhaler will increase cigarette abstinence more in heavier smokers.

Aim/Objective 3: To identify factors that determine which women benefit most from the use of nicotine inhaler for smoking cessation during pregnancy

Hypothesis 4: We hypothesize that birth weight will be negatively correlated with CPD and exhaled CO at the end of pregnancy, and that smoking cessation or reduction in the third trimester will explain the effect of treatment group on birth weight. We will also explore the interrelations among birth outcomes, tobacco exposure, and other promising biomarkers.

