Aim/Objective 4: To explore mechanisms by which the nicotine inhaler increases birth weight and gestational age.

4. Study Design & Procedures:

Study design: This is a randomized, double blind, placebo-controlled trial of the safety and efficacy of the nicotine inhaler in combination with behavioral counseling for smoking cessation during pregnancy. A total of 360 pregnant smokers will receive nicotine or placebo inhaler medication (1:1 ratio) for 6 weeks followed by a 6-week taper, with double-blind treatment conditions maintained throughout the study. Smoking cessation counseling and medication will be provided by a nurse at each ambulatory clinic. Nurses will be closely supervised by a psychologist with extensive expertise in smoking cessation ([name]), an obstetrician ([name] or [name]), and [name].

Overview of the behavioral intervention: The behavioral intervention, which will be utilized in both arms of the proposed study, exceeds many of the augmented interventions described in the USPHS guidelines [38]. The behavioral counseling will include a 35-minute counseling sessions at each of the first two visits, and 10 minutes of smoking cessation counseling at subsequent visits, delivered by the study nurses.

Overview of pharmacotherapy intervention: We will administer a 6-week course of therapy, consistent with instruction on the package insert. Dosage recommendations are based on the literature and on our pilot data, and will vary according to the level of maternal smoking. Pfizer Pharmaceuticals has agreed to supply us with nicotine inhaler and placebo treatments (see letter of support). To enhance compliance and to confirm patient reports and proper inhaler use, subjects will be asked to keep a daily diary of the number of cartridges used and to return all cartridges at the next study visit. Subjects will be instructed to bring medication and empty cartridges to next visit when they receive their reminder telephone call regarding upcoming appointments. For convenience, subjects will receive a plastic container to transport study drug. At Visit 5 (6 week visit), patients will be instructed on an individualized basis to taper their use over the next 6 weeks. If a study subject does not quit smoking

Nicotine Replacement for Smoking Cessation during Pregnancy

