Mediational analyses: Measures of nicotine withdrawal, depressive symptoms, and perceived stress measured at baseline and at each study visit will serve as potential mediators. Specifically, we expect that the nicotine inhaler will result in a greater reduction in nicotine withdrawal symptoms than placebo, and that these variables will partially mediate the effects of treatment. Tests of mediation using the Mplus statistical package [80], which allows for missing data, will provide evidence of a causal link between treatment, the mediator variable(s), and the outcomes.

Specific Aim 4: To explore mechanisms by which the nicotine inhaler increases birth weight and gestational age. Based on the results of our completed study [3] and another NRT trial [7], we anticipate that offspring born to women in the inhaler group will have a higher birth weight and gestational age than those in the placebo group. If NRT increases birth weight, potential mediators of this effect will be explored. Measures of tobacco use (cigarettes per day, and exhaled CO) and 7 day point prevalence abstinence at each study visit will serve as potential mediators. Specifically, we expect that the nicotine inhaler will result in cessation or a greater reduction in CPD or exhaled CO, and that these variables will partially mediate an increase in birth weight. We will use a Mplus statistical package to perform mediational analyses [80]. The same analytic approach will be used separately to examine gestational age (in wk).

Depending on whether smoking cessation or reduction mediates the effect of NRT on birth weight, the appropriate variable will be used a predictor variable in an additional mediational model that examines potential biomarkers (**C-reactive protein or sICAM**) as mediators of birth weight or gestational age. Specifically we will test with Mplus statistical software whether cessation (or reduction) influences a change in biomarker concentration and whether this increases birth weight or gestational age.

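### The correlation and biomarker parts of Hypothesis 4 carry no condition, but the Aim 4 smoking and biomarker analyses depend on an undefined increase in birth weight with treatment

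*Combined protocol and SAP*

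**What the plan says.** In section 3 (Hypotheses, aims and objectives), Hypothesis 4 has three parts. The first is an association: "birth weight will be negatively correlated with CPD and exhaled CO at the end of pregnancy". The second is a mediation claim: "smoking cessation or reduction in the third trimester will explain the effect of treatment group on birth weight". The third is the biomarker question: "We will also explore the interrelations among birth outcomes, tobacco exposure, and other promising biomarkers". Only the second refers to a treatment effect. The Aim 4 objective also presupposes one: "To explore mechanisms by which the nicotine inhaler increases birth weight and gestational age".

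Section A 3 (Importance of Measuring Biomarkers) says "We will evaluate specific biomarkers of smoking-related harm during pregnancy". It presents C-reactive protein and sICAM as possible links between tobacco exposure and poor birth outcomes. It also values them as surrogate measures of risk for other products. Neither purpose needs a birth-weight effect of the inhaler.

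Under Method(s) of data analysis, Specific Aim 4, the smoking measures (cigarettes per day, exhaled CO, 7-day abstinence) are examined under a condition: "If NRT increases birth weight, potential mediators of this effect will be explored". The biomarker model follows from that step: "Depending on whether smoking cessation or reduction mediates the effect of NRT on birth weight", a smoking variable is chosen to enter it. The last paragraph of that section adds an analysis of cotinine, separate from tobacco reduction, on pregnancy outcomes and biomarkers, with no condition. The sample-size section calls Aim 4 exploratory and gives no calculation for it.

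**The concern.** Two of the three parts of Hypothesis 4 can be answered in all women, whatever the arms show. Yet the plan reaches the smoking measures, and through them the two biomarkers, only after treatment has increased birth weight. The analyses for Aims 1 to 3 do not relate birth weight to cigarettes per day or exhaled CO either. The cotinine analysis cannot stand in for them, because in the inhaler arm cotinine also reflects the medication.

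A total arm effect is also a weak screen for a pathway. If treatment acts through extra quitters, the arm difference is the per-quitter gain diluted by the small share of women who quit because of treatment. If a benefit of cessation and a direct effect of nicotine work in opposite directions, the total can be near zero while both are present. Following the plan as written could leave a stated hypothesis and a main purpose of the blood samples without an analysis.

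**Working it through.** **Inputs from the protocol.**
- Quit rates 14.9% and 26.9%, 180 per arm, two-sided 5% level, power 0.80; birth-weight difference about 300 g, SD 607 g (Sample size and justification).
- Two-sample t-test for birth weight (Specific Aim 2.b).
- Earlier gum trial: 3287 vs 2950 g and 18% vs 14.9% quitting at 32-34 weeks; patch trial: 186 g (A.2.b).
- Data from 75% of subjects in the earlier trial (Incentives), which would be 135 per arm here.

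**Assumption not in the protocol.** Grams gained per quitter, called g, varied from 100 to 400. The model takes cessation as the only path, with no direct effect of nicotine and no confounding of quitting with birth weight.

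**The plan's own figure.** Odds 0.149/0.851 = 0.175; times 2.1 = 0.368; 0.368/1.368 = 26.9%. The two-proportion test with pooled variance and 180 per arm has power 0.802. This reproduces.

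**Chance that the condition is met.** The arm difference is D = (0.269 − 0.149) × g = 0.12g. The standard error is 607 × √(2/180) = 64.0 g. If *increases* means a significant result in favour of nicotine, the chance is 1 − Φ(1.96 − D/64.0). If it means any positive estimate, the chance is Φ(D/64.0).

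**Chance that the indirect effect is significant.** Simulated trials with birth weight = g × quit + normal error, SD 607. Both the arm-to-quitting test and the quitting coefficient, with arm in the model, must be significant.

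| g (assumed) | D | Met, significance | Met, positive estimate | Indirect effect significant |
|---|---|---|---|---|
| 100 g | 12 g | 3.8% | 57% | about 19% |
| 150 g | 18 g | 4.7% | 61% | about 38% |
| 200 g | 24 g | 5.6% | 65% | about 57% |
| 250 g | 30 g | 6.8% | 68% | about 71% |
| 400 g | 48 g | 11.3% | 77% | about 80% |

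The last column cannot go much above 0.80, because the arm-to-quitting test itself has power 0.80. With 135 per arm and 250 g, the indirect effect is significant in just over half of trials (52% to 53% across runs), and a significance condition is met in 6.0%.

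**Larger total effects.** With the same formula, a significance condition is met in 50% of trials at 125 g, 65% at 150 g, 83% at 186 g and 99.7% at 300 g.

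**Can cessation alone produce 300 g?** In the gum trial, 337 g came with a 3.1-point difference in quitting: 337/0.031 ≈ 10,900 g per extra quitter. That is not credible, so an effect of that size needs another route, such as reduction or a direct effect.

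**Unconditional association.** For a correlation r (assumed), power is Φ(atanh(r) × √(N − 3) − 1.96). At r = 0.15 it is about 0.81 with 360 women and about 0.69 with 270. At r = 0.10 with 360 it is 0.47.

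**The case against.** A reader might infer that all of Hypothesis 4 is unconditional. It is not. Its mediation clause and the Aim 4 objective presuppose a treatment effect, and conditioning that step on an effect matches their wording.

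A reader might also infer that the pathway would go unexamined in most trials. The documents do not support that as a general statement. It needs a significance reading of a word the plan does not define. It also needs cessation to be the only path, whereas Hypothesis 4 names cessation or reduction, and the gum trial found greater reduction on nicotine without a significant difference in quitting. If reduction lifts the total to about 125 g, a significance condition is met in about half of trials. At the planning difference of 300 g it is almost always met. The per-quitter gain is an assumption, and with a small gain or incomplete data the indirect effect would often be missed too.

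Three further limits stand. The sentence that introduces the biomarker model reads at least as naturally as a choice between cessation and reduction as it does a second hurdle. The cotinine analysis partly examines exposure, biomarkers and outcomes outside the condition. And the condition does not bias the reported total effect by selection, because Specific Aim 2.b compares birth weight in every case.

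What the objection leaves intact is that the association with cigarettes per day and exhaled CO has no stand-alone analysis, and that the smoking-to-biomarker-to-birth-weight models depend on an undefined result. Exploratory status lowers the stakes, but it also removes any error-control reason for the condition.

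**Conclusion.** The point holds for the correlation and biomarker parts of Hypothesis 4. The hypotheses state them without condition, while the Aim 4 analysis makes the smoking and C-reactive protein/sICAM models depend on an increase in birth weight that is never defined.

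How often this matters depends on the mechanism and the reading. At one end, with cessation alone, 100 to 400 g per quitter and a significance criterion, the condition is met in about 4% to 11% of trials, against about 19% to 80% for a significant indirect effect. At the other end, at total differences of 186 g or 300 g, it is met in 83% or 99.7%. A positive-estimate reading lies between, at about 68% for 250 g. These figures assume complete data on 360 women unless stated, an SD of 607 g and no confounding of quitting with birth weight.

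No primary, safety or birth-outcome comparison is affected. This is a cheap improvement.

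**What to change.** Delete the condition in the Specific Aim 4 analysis. Whatever the birth-weight comparison shows:

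1. Regress birth weight and gestational age on cigarettes per day and, separately, on exhaled CO at 32-34 weeks, in all women, with treatment arm in the model.
2. Estimate the indirect effect of treatment through cessation and through reduction.
3. Fit the C-reactive protein and sICAM models with arm included.

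Label all of this exploratory, as Aim 4 already is, and report estimates with intervals. The smoking and biomarker comparisons are not randomised, so they should be described as associations. If any condition is kept, define what counts as an increase.

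The cost is a change of wording and a few more models on data already to be collected. The downside is a few more exploratory results to report.

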5. **PHQ:** We have chosen to identify major psychopathology using the PRIME-MD Patient Health Questionnaire [74]. This questionnaire consists of nine questions that screen for depression. Each item yields a score of 0-3, and the highest possible total score for all items is 27. The scale can be used longitudinally to identify trends in depressed mood. Subjects with evidence of suicidal ideation or any other severe, acute psychiatric symptom (e.g., psychosis) will be excluded from the study. Subjects who answer “more than half the days” to 5 or more items will be excluded from the study. Since the questionnaire relies on patient self-report, all responses will be verified by the principal investigator, if a subject answers “more than half the days” to 5 or more items to confirm exclusion is warranted.
6. **Self-efficacy questionnaires:** Evaluates confidence to resist smoking across a number of different situations [60]. The scale yields a total score, as well as subscores for positive & negative affect situations, and habit/craving items. This scale has been a strong predictor of smoking outcomes in previous studies [73].
7. **Exhaled carbon monoxide measurement.** Subjects will be asked to blow into a machine that measures CO in parts per million (ppm). Levels <9 ppm are consistent with cigarette abstinence [69].
8. **Urine sample:** A urine sample will only be collected at BL, V2, V5, and V6 and analyzed only if serum can not be obtained. Urine will be tested using the NicAlert method.

The screening visit is expected to take 1.5 hours. The participant will be given a handout to record cigarette intake prior to subsequent study visits.

Study Procedures and who will perform them:

Baseline: Eligible subjects scheduled to return for a baseline (i.e. randomization) visit approximately 1 week after screening (+ 14 Days). The study nurse will review the patient's medical history and confirm current medical and pregnancy history. She will discuss each case with the study obstetrician (at the performance site) who will sign off on entry of subject into the study.

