1. **Randomization assignment:** As previously noted randomization will be 1:1 for nicotine inhaler or placebo assignment. To ensure comparability of subjects in the treatment groups, we will employ urn randomization, a probabilistic balancing procedure that assigns patients to conditions so that groups are balanced on key variables [57]. Key variables that we would like to balance groups on include history of preterm delivery (yes/no), gestational age at study entry (<19 weeks vs. \geq 19 weeks), and number of CPD (<10 vs. \geq 10).

The nurse will fax key variables for a given subject to the research pharmacist at UCONN who will enter these variables into a specially developed computer algorithm by that is

the basis for the urn randomization procedure. In this way, treatment groups will be comparable on important features that may influence treatment outcome. Once the pharmacist enters these variables, the computer assigns a treatment assignment. The pharmacist will communicate with the study nurse (by fax or e-mail) which medication box # to dispense to the subject.

2. **Maternal blood draw** (approximately 15 cc): Venipuncture will be performed using standard sterile blood drawing techniques by trained personnel. Serum will be separated on site and stored at -20 degrees C on at least a biweekly basis until transfer to UCHC where it will be stored at -70 C. Samples will be measured for cotinine, the major metabolite of nicotine, and a reliable measure of overall nicotine intake. Cotinine will be measured by GC/Mass Spectrometry at Yale University. UCHC Core Lab will ship transport tubes to Yale after subjects' Week 2 visit. If the subject does not come to Visit 2, the blood will be obtained at the next scheduled visit. Serum will also be measured for hydroxycotinine/cotinine ratio, the rate at which nicotine is metabolized. Samples will be shipped in compliance with DOT/IATA regulations (dry ice, Fed-Ex Overnight Express, etc.). The results will be emailed to the P.I. and the study coordinator at each site. Serum will measured for high sensitivity C-reactive protein (Siemens Medical Diagnostics, Los Angeles CA) by solid phase chemiluminescent immunometric assay and sICAM (R&D systems, Minneapolis, MN) measured by sandwich EIA in the GCRC core laboratory. If possible, this blood draw will be incorporated with other routine prenatal blood draws.
3. **Urine sample:** Urine will only be used as a backup for cotinine if necessary.

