Visit 1: Subjects seen approximately 1 week (+/- 4days) after their quit date to assess adverse effects and progress in smoking cessation. At this visit, the nurse administers behavioral counseling (35 minutes) and assesses medication usage. The study coordinator will administer all assessments.

1. Vital signs and weight
2. Exhaled CO measurement
3. Nicotine Use Survey
4. Questionnaires: MNWS
5. Adverse Effects Inhaler & Adverse Events
6. Concomitant Medication
7. Inhaler usage: We will collect used cartridges from patient and review diary of inhaler usage.
8. Counseling: The second counseling session is scheduled 1 week after the quit date. The primary focus of this session will be to assess reactions to the initial session, smoking status, and the effectiveness of the intervention, and to discuss strategies to deal with smoking urges and tobacco withdrawal symptoms. Subsequent sessions will focus on achieving or maintaining abstinence, increasing self-efficacy, skills training (depending on the patient's smoking status), and providing support.

This visit will take 45 minutes.

Visits 2 (2 weeks after the quit date +/- 4 days). The following items will be assessed by research nurse.

1. Vital signs and weight
2. Exhaled CO measurement
3. Maternal Blood draw (15 cc) If possible, this blood draw will be incorporated with other routine prenatal blood draws. Will collect urine as backup.
4. Nicotine Use Survey
5. Questionnaires: MNWS, PHQ
6. Adverse Effects Inhaler & Adverse Events
7. Concomitant Medication
8. Inhaler usage: We will collect used cartridges from patient and review diary of inhaler usage.
9. Dispensement: We will dispense a 2 week supply of study medication, if needed.
10. Counseling (10 Minutes): Counseling will focus on achieving or maintaining abstinence (set another quit date if necessary), increasing self-efficacy, skills training (depending on the patient's smoking status), and providing social support, and using inhaler to combat urges to smoke.

This visit will take 45 minutes. After the session the nurse will send the two maternal serum samples for cotinine analyses. If the visit 2 sample exceeds that of baseline by 40%, the study nurse will call the patient and advise a decrease in inhaler dosage that will be recommended by [name].

Visit 3 (3 weeks after the quit date +/- 4 days). The following items will be assessed by research nurse.

1. Vital signs and weight
2. Exhaled CO measurement
3. Nicotine Use Survey

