- ii. enrolled subjects met eligibility criteria and
- iii. all study procedures are completed as outlined in the study protocol.
- c. Verification of protocol adherence and verification that all deviations from the protocol are documented with an explanation of circumstances.
- d. Verification that subjects failing to complete the study and the reason for each failure are noted
- e. Performance of a serious adverse event review; with emphasis on the proper follow-up and reporting of adverse events
- f. Verification of investigational product accountability (review drug handling, drug accountability, drug temperature logs, review each chart for physician sign off).
- g. Performance of a review of the study regulatory file
- h. Performance of a review of the data and safety monitoring plan meeting minutes/notes.

Timetable:

Expected Start Date: **12/1/10**

Timeline of Study Procedures (including time to administer questionnaires and other procedures):

Assessment	Pt time (min)	Screen	Baseline (wk -1 before QD)	Visit 1 (wk 1 after QD)	Visit 2 (wk 2 after QD)	Visit 3 (wk 3 after QD)	Visit 4 (wk 4 after QD)	Visit 5 (wk 6 after QD)	Visit 6 (32-36 wk GA)	Visits 7** & 8 (1 & appox. 6 months postpartum)
Visit window				+/- 4	+/- 4	+/- 4	+/- 4	+/- 10	N/A	V.7(+/- 7), V.8(+/- 14)
Demographics	2	X								
Smoking and FTND	10	X								
Medical Screen	20	X								
Social Support and Self-Efficacy Questionnaires	5	X								
PRIME-MD PHQ	2	X	X		X			X	X	
Vital signs & Weight	5	X	X	X	X	X	X	X	X	
Nicotine Use Survey	1	X	X	X	X	X	X	X	X	X
Cotinine, Biomarkers, and hydroxycotinine/cotinine ratio	5		X		X			X	X	
Carbon monoxide	2	X	X	X	X	X	X	X	X	X
Urine sample as backup	5		X		X			X	X	
Smoking cessation counseling ^a	10		X ^a	X ^a	X	X	X	X	X	
MNWS	2		X	X	X	X	X	X		

Nicotine Replacement for Smoking Cessation during Pregnancy

Adverse Effects	2		X	X	X	X	X	X	X	
Concomitant Medication	2	X	X	X	X	X	X	X	X	
Medication Dispensement	5		X		X		X			
Inhaler Usage	2			X	X	X	X	X	X	
Assignment Question	1					X				
Birth Outcomes*	30									

*Information obtained by chart review by study personnel; ** phone interview; GA = Gestational Age; QD=Quit Date; ^a Counseling will be approximately 35 minutes for the first 2 sessions, and 10 minutes for subsequent sessions; ^b Proposed medication dispensing times. If the subject misses a visit, drug may be dispensed at a subsequent visit.

Timeline of Performance Goals for the entire study:

Activity	Year 1	Year 2	Year 3	Year 4	Year 5

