
If for any reason we are unable to obtain blood for serum cotinine, overall nicotine exposure will be assessed with the nicalert urine test at each visit. With this system there are 5 levels of exposure (Level 0: 1-10, Level 1: 10-30, Level 2: 30-100, Level 3: 100-200, Level 4: 200-500, Level 5: 500-1000, and Level 6 1000 plus) and an increase in any

Nicotine Replacement for Smoking Cessation during Pregnancy

level would be consistent with an increase in exposure. This type of monitoring was utilized in one clinical trial that was monitored by the FDA to estimate overall nicotine exposure in pregnant women (33).

- 5) **Pregnancy adverse problems**--We are only including subjects with chronic stable medical problems and no imminent pregnancy problems will be enrolled into the study. If there are any questions regarding current pregnancy problems the case will be discussed with the primary care provider (after obtaining consent from subject) and also reviewed with study obstetricians. We are monitoring nicotine exposure in both groups which may decrease the risk of adverse pregnancy problems. Additionally, women receive a comprehensive behavioral intervention designed to help them quit smoking, which should decrease the risk of pregnancy adverse effects. Women are monitored closely throughout the study and if an adverse event occurs consultation and treatment will be coordinated with their obstetrician.
- 6) **Withdrawal and worsening mood symptoms**-- although uncomfortable, nicotine withdrawal symptoms (irritability, craving for cigarettes, insomnia, increased appetite/weight gain, depressed mood) do not propose a significant medical risk. Nicotine replacement is designed to relieve withdrawal symptoms. Some studies suggest that especially persons with a history of depression may be at an added risk of depression with smoking cessation; however, we did not observe this in our last study (Oncken et al., 2008). If depressive symptoms occur (as evidenced by patient report or worsening symptoms on the beck questionnaire), the subject will be seen by a masters level counselor or [name]. [name] will help devise the treatment plan. Subjects who experience significant increases in depressed mood will be referred for further evaluation and treatment.

3. Describe circumstances that may lead to a subject being removed from the trial by the PI, e.g. due to failure to follow study procedures, and the process for doing so:

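### The urine back-up rule needs a baseline NicAlert level, and the plan does not secure one for a woman whose baseline serum is obtained but whose Visit 2 draw fails

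*Combined protocol and SAP*

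**What the plan says.** **When urine is collected and tested.** Screening Procedures, item 8, states: "A urine sample will only be collected at BL, V2, V5, and V6 and analyzed only if serum can not be obtained". It adds: "Urine will be tested using the NicAlert method". The Baseline section, item 3, says: "Urine will only be used as a backup for cotinine if necessary". The Visit 2 blood-draw item says: "Will collect urine as backup". The timeline table has a row "Urine sample as backup", marked at Baseline, Visit 2, Visit 5 and Visit 6.

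**What the urine result is for.** Appendix A, item 2.B.4, says that when blood for cotinine is unavailable, whatever the cause, "overall nicotine exposure will be assessed with the nicalert urine test at each visit". A move up in level then counts as increased exposure. The visit to compare against is not named. The scale is introduced as "With this system there are 5 levels of exposure (Level 0: 1-10, Level 1: 10-30" and continues to Level 6, which is open-ended from 1000.

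**The serum rule.** In the same item, an on-treatment serum cotinine more than 40% above the woman's baseline or screening value counts as an increase. This rule needs serum on both sides.

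**Storage and later samples.** Baseline, item 2, gives storage conditions for serum only. It also says that a woman who misses Visit 2 is bled at her next scheduled visit. At Visits 5 and 6, serum goes for cotinine analysis only if the nurse finds a significant change in smoking or inhaler use.

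**The concern.** A rule based on a rise needs two measurements on the same scale. Serum cotinine is a continuous concentration and NicAlert gives an ordered band, and the plan has no rule for comparing one with the other. If baseline serum is obtained, nothing in the screening or baseline text prompts a test of the baseline urine. If the Visit 2 draw then fails, the Visit 2 strip has no earlier strip beside it.

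What is at stake is a safety check. Appendix A describes pregnant women as a vulnerable population and gives the aim of keeping exposure on treatment from exceeding that from smoking. The urine test is there for women whose blood cannot be obtained, so it should work after a single failed draw. Sample size, power and the primary abstinence analysis are not affected.

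**Working it through.** The plan gives no figure on this point to reproduce. The check sets the rules side by side and then gives an illustrative scale.

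**Step 1: the four serum patterns.** Item 8 does not say at which visit serum must fail. There are two readings: each visit is judged on its own, or the woman is switched to urine once a draw fails (the Appendix A wording).

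| Serum obtained at | Each visit judged separately | Woman switched to urine |
|---|---|---|
| Baseline and Visit 2 | 40% serum rule | 40% serum rule |
| Neither | Strip against strip | Strip against strip |
| Baseline only | Serum, then strip: no rule | Strip against strip only if baseline urine was kept |
| Visit 2 only | Strip, then serum: no rule | Strip against strip, since Visit 2 urine is collected and can be tested that day |

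The third row is the weak one under both readings. By Visit 2 the baseline visit has passed, so the second reading rescues the rule only if the baseline sample still exists.

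**Step 2: does another provision close the third row?**
- Retention of urine: none is described. The Monitoring and Auditing section mentions freezer logs for specimens in general, without naming urine.
- The catch-up draw: it is written for a woman who does not come to Visit 2, not for one who attends and cannot be bled.
- Serum at Visits 5 and 6: its analysis depends on the nurse's judgement of a change, and Appendix A describes increased smoking by reference to Visit 2. It is a later, conditional check.

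**Step 3: scale.** Inputs: N = 360 (Study design) and a per-visit draw failure rate f. The documents give no f, so 5% and 10% are assumptions. With independent failures, the expected number with baseline serum but no Visit 2 serum is N × f × (1 − f):
- f = 5%: 360 × 0.05 × 0.95 = 17.1
- f = 10%: 360 × 0.10 × 0.90 = 32.4

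For comparison, serum missing at both visits is N × f²: 360 × 0.0025 = 0.9 and 360 × 0.01 = 3.6.

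Independence is also an assumption. For the same f at both visits, the baseline-only count cannot exceed N × f (18 or 36), and it falls towards zero if the same women fail both times.

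**Step 4: the level list.** Levels 0 to 6 are seven levels, against a stated five. Adjacent bands share the boundaries 10, 30, 100, 200, 500 and 1000, so a reading on a boundary belongs to two levels. Level 6 has no upper limit, so a woman at Level 6 at baseline cannot move up.

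**The case against.** The strongest reply is that the plan never says urine is tested only at the visit where serum fails. Item 8 names no visit, and Appendix A can be read as moving the woman to urine throughout. Baseline urine is scheduled for every woman, so a sample should exist to test. On this view the plan is silent about retention, and silence does not make the rule unworkable. This stands in part. Testing visit by visit is an inference, although it is the natural one, and a site that happened to keep baseline urine could apply the rule. But nothing tells a site to keep it.

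A reader might infer more than the documents support:
- That the reverse failure (no baseline serum, Visit 2 serum obtained) is just as unpaired. It need not be. Baseline urine is then tested, and the Appendix A wording allows a strip at Visit 2 on urine already collected.
- That women who are hard to bleed get no usable check. Such women are more likely to fail both draws, which is a pattern the rule does handle, and conditional later serum remains possible.
- That draws could fail in 25% of women, because the Incentives paragraph reports data from 75% of subjects in the earlier trial. That figure describes overall data collection. A woman who does not attend gives neither blood nor urine.

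The miscounted levels and shared boundaries are fairly called editorial. The open top level is a limit of the rule itself, though the documents do not say how many women would start there.

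**Conclusion.** The concern holds in a limited form. Appendix A's urine rule depends on an earlier NicAlert level, but the screening and baseline text do not call for one when baseline serum is obtained. No provision keeps the baseline urine for later testing, and no comparator visit is named. As written, the rule cannot be applied to a woman with baseline serum who attends Visit 2 and cannot be bled, unless her baseline urine happens to have been kept and is then tested.

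The number of such women is unknown. About 17 to 32 of 360 is an illustration that rests on assumed, independent failure rates of 5% to 10%. The procedural gap does not depend on those rates. Separately, the rule cannot register a rise in a woman who starts at Level 6.

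**What to change.** 1. In Screening Procedures, item 8 (and Baseline, item 3, to match), require the NicAlert strip to be run and recorded on every baseline urine. Alternatively, require that the urine be kept and tested if a later serum draw fails, and state the storage conditions.
2. In Appendix A, item 2.B.4, name baseline as the comparator and require strip to be compared with strip. State that this includes running the Visit 2 strip when baseline serum was not obtained.
3. Reconcile testing at every visit in Appendix A with the four collection visits in item 8 and the timeline table.
4. Correct the number of levels, and make the bands non-overlapping.
5. State how exposure is assessed for a woman already at Level 6 at baseline.

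The cost is up to 360 strips on urine already scheduled for collection, plus wording. Items 1 and 2 need no new visit or sample. Nothing here proposes what should be done clinically when a rise is found.
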